8.2.4.2. Tissue Collection for Tailoring Biomarker Studies

Tumor and plasma specimens will be collected throughout the study for the assessment of predictive biomarkers related to the activity of LY3009120, for exploratory research on new biomarkers related, but not limited, to the Raf pathway, and for evaluation of tumor specific biomarkers depending on evolving science.

Archived tissue: Precut, unstained slides from any available archival specimen of the patient's tumor will be ~~required from patients enrolled in Part B and will be requested~~ (but not required) for patients enrolled in Part A.

Study tumor biopsies: ~~In addition, patients enrolled in Part B Cohort A (Section 6.1.1 Inclusion Criteria [3]) will undergo a mandatory pre-treatment tumor biopsy before receiving the first dose of study drug.~~

For Part A and Part B: **Mandatory tumor biopsies will be collected as indicated in Section 8.2.4.1.**

Tumor tissue biopsies will be taken either by core needle or excisional biopsy. The size of the sample will be dependent upon the procedure utilized to obtain the sample. These biomarker-related studies will include, but may not be limited to, protein and/or genetic analyses of the tumor specimen.

Attachment 1. Protocol JBDA Study Schedule

Part B: Baseline Assessments

Relative Day Prior to Day 1 of Cycle 1	≤28	≤14	≤3	Comments
Informed Consent				Informed Consent Form signed (prior to performance of any protocol-specific tests/procedures)
Chest X-ray	X			May be omitted in patients having a chest CT scan for their radiological tumor assessment
Radiological Tumor Assessment	X			
Medical History		X		Including any alcohol/tobacco habits
Physical Exam		X		
Vital Signs		X		Including temperature, blood pressure, pulse rate, respiration rate
ECOG Performance Status		X		
ECG		X		Central collection and storage
Hematology (local)		X		
aPTT, PT, PT/INR (local)		X		
Serum Chemistry		X		
Urinalysis (local)		X		
Tumor Measurement (Palpable or Visible)		X		
CTCAE v 4.0 Grading (Preexisting conditions)		X		To be reported only after study eligibility is confirmed.
Concomitant Meds		X		
Exploratory blood plasma sample		X		EDTA tube collection after eligibility confirmed
Study Tumor Biopsy (Part B, Cohort A only all cohorts)		X		Biopsy should be taken only after study eligibility is confirmed (mandatory).
Archived Tumor Sample	X			Paraffin-embedded tumor tissue (mandatory). Sent after study eligibility is confirmed.
Pregnancy Test (local)			X	Negative results required prior to Cycle 1, Day 1. Only to be performed on women of childbearing potential.
Eye Safety Assessments	X			
Dermatological Evaluation		X		

Abbreviations: aPTT = activated partial thromboplastin time; CT = computed tomography; CTCAE = Common Terminology Criteria for Adverse Events; ECG = electrocardiogram; ECOG = Eastern Cooperative Oncology Group; Meds = medications; PD = pharmacodynamic; PT/INR = prothrombin time/international normalized ratio.

Part B: During and Poststudy Assessments

Relative Day Within a Cycle	Cycle 1					Cycle 2					Cycle 3-n		Follow-Up		Comments
	1	8	15	22	28	1	8	15	22	28	1	28	Visit 801	Visits 802, 803, and 804 (Long-term Follow-up)	
LY3009120		X					X				X				
Physical Exam	X	X	X	X		X					X			X	After C1D1, ± 3 days while on treatment; Will not need to be repeated if performed ≤ 3 days from C1D1.
Eye Assessments					X						X				At baseline, at the end of Cycle 1 and Cycle 2, and every 2 cycles afterwards (end of C4, C6, and so on) up to 7 days before start of next cycle, and at other time points if clinically indicated. Assessment can also be performed on the D1 of the next cycle (predose).
Dermatological Evaluation											X			X	At baseline, every 2 cycles while on therapy, and every 2 months for up to 6 months following discontinuation of LY3009120.
Weight	X					X					X				After C1D1, ± 3 days while on treatment
Vital Signs	X	X	X	X		X					X				Temperature, PR, RR, BP. After C1D1, ± 3 days while on treatment.
ECG	X		X			X					X				In cycle 1 only, on days with PK assessments ECGs will be performed before patients receive morning dose of study drug at the site and 3 hours post-dosing After C2D1, ± 3 days while on treatment.

Relative Day Within a Cycle	Cycle 1					Cycle 2					Cycle 3-n		Follow-Up		Comments
	1	8	15	22	28	1	8	15	22	28	1	28	Visit 801	Visits 802, 803, and 804 (Long-term Follow-up)	
Hematology	X	X	X	X		X	X	X	X		X		X		After C2D1, ± 3 days while on treatment; On days with PK assessment it will be performed before patients receive morning dose of study drug at the site.
Serum Chemistry	X	X	X	X		X	X	X	X		X		X		After C2D1, ± 3 days while on treatment; On days with PK assessment it will be performed before patients receive morning dose of study drug at the site.
Urinalysis	X					X					X				After C1D1, ± 3 days while on treatment; will not need to be performed if completed less than 3 days before Cycle 1 Day 1.
CTCAE v 4.0 Grading	X					X					X	X		Throughout study as needed.	
Concomitant Meds	X					X					X	X		Throughout study as needed.	
ECOG Performance Status	X					X					X				After C1D1, ± 3 days while on treatment
PK Sampling	X		X	X	✗						X		X		See PK Sampling Attachment 4 for exact timing.
Tumor Measurement (Palpable or Visible)	X					X					X		X		After C1D1, ± 3 days while on treatment
Radiological Tumor Assessment										X		X	X		Approximately every 8 weeks (every other cycle, end of C2, C4, and so on). Up to 7 days before start of next cycle.
Urine Metabolite Collection	X														To be collected from up to 3 patients enrolled in Part B; not a protocol violation if not collected.

	Cycle 1					Cycle 2					Cycle 3-n		Follow-Up	Comments	
Relative Day Within a Cycle	1	8	15	22	28	1	8	15	22	28	1	28	Visit 801	Visits 802, 803, and 804 (Long-term Follow-up)	Visit 801 is 30 days (\pm 3 days) after last dose of study drug; Visits 802, 803, and 804 are each 2 months in duration and will start after Visit 801.
Pharmacogenetic blood sample, stored (mandatory)	X														
Exploratory blood plasma sample				X	X					X		X	X		To be collected in all patients in Part B for a maximum of 9 to 12 cycles.
Study Tumor Biopsy			X												Can be \pm 5 days

Abbreviations: BP = blood pressure; CTCAE = Common Terminology Criteria for Adverse Events; ECG = electrocardiogram; ECOG = Eastern Cooperative Oncology Group; PK = pharmacokinetic; PD = pharmacodynamic; PR = pulse rate; RR= respiration rate.

Attachment 4. Protocol JBDA Pharmacokinetic and Exploratory Blood Plasma Sampling Schedule

Pharmacokinetic Sampling Schedule For Patients in Part B

Sample Number	Cycle	Day	PK Sampling Time for LY3009120 ^a	Exploratory Blood Sample ^b	Urine Sampling (Part B only- up to 3 patients)
1	1	1	predose	X	0 to 10h pooled samples (end time to coincide with PK blood draw)
2	1	1	0.5		
3	1	1	1		
4	1	1	2		
5	1	1	4		
6	1	1	6		
7	1	1	8		
8	+	+	10		
9	1	15	predose		
10	1	22	predose	X	
11	+	28	predose	X	
12	+	28	0.5		
13	+	28	1		
14	+	28	2		
15	+	28	4		
16	+	28	6		
17	+	28	8		
18	+	28	10		
19	2	28	predose	X	
20	3-n	28	predose	X	
21	Follow-up (Visit 801)	-	-	X	

^a Predose PK samples should be collected prior to the morning dose, and all samples collected as close to the scheduled times as possible.

^b Baseline exploratory blood plasma sample (EDTA tube) will be collected ≤ 14 days before first dose of LY3009120 after eligibility is confirmed. Samples will also be collected during treatment predose on Day 22 of Cycle 1, and Day 28 of each cycle thereafter; and during follow-up Visit 801. During treatment this sample will be collected for a maximum of 9 to 12 cycles.

4.1. Primary Objective

The primary objective of this study is to determine a recommended Phase 2 dose of LY3009120 that may be safely administered to patients with advanced and/or metastatic cancer.

4.2. Secondary Objectives

The secondary objectives of this study are:

- to characterize the safety and toxicity profile of LY3009120.
- to estimate the pharmacokinetic (PK) parameters of LY3009120.
- to document any antitumor activity observed with LY3009120.

4.3. Exploratory Objectives

The exploratory objectives of this study are:

- to explore pharmacodynamic (PD) biomarkers.
- to explore biomarkers related to the safety and efficacy of LY3009120.

5. A Priori Statistical Methods

5.1. Endpoint Definitions

5.1.1. Safety Endpoints

All patients who receive at least 1 dose of LY3009120 will be evaluated for safety and toxicity. Safety measures that will be used in the study include adverse event (AE), dose limiting toxicity (DLT), clinical laboratory test results, vital signs and electrocardiograms (ECG). In addition, after each cohort, the toxicity-band method will be used to summarize the posterior distribution of probability of a DLT. All AEs will be classified and graded using the National Cancer Institute Common Terminology Criteria for Adverse Events (NCI CTCAE) version 4.0.

Dose Limiting Toxicity:

Dose-limiting toxicity (DLT) is defined as an adverse event (AE) during Cycle 1 for a patient enrolled in Part A (Dose Escalation) that is possibly related to the study drug and fulfills any one of the following criterion using the National Cancer Institute's (NCI) Common Terminology Criteria for Adverse Events (CTCAE) v4.0:

- \geq CTCAE Grade 3 non-hematological toxicity. Exceptions will be made for:
 - Nausea, vomiting, diarrhea, or constipation that can be controlled with appropriate care. Grade 3 and Grade 4 nausea, vomiting, or diarrhea should be considered DLT if persisting more than 48 hours despite maximum supportive intervention.
 - Grade 3 elevations of ALT and/or AST lasting fewer than 8 days, without evidence of other hepatic injury, in the setting of preexisting hepatic metastasis and baseline elevation of these values, may not be considered a DLT if agreed by the study investigator and Lilly CRP.
- CTCAE Grade 4 hematological toxicity of >5 days duration.
- Grade 4 thrombocytopenia of any duration
- Grade 3 thrombocytopenia with bleeding
- Grade 3 febrile neutropenia
- Any other significant toxicity deemed by the primary investigator and Lilly clinical research personnel to be dose limiting (for example, any toxicity that is possibly related to the study medication that requires the withdrawal of the patient from the study during Cycle 1).

Investigators, together with the Lilly CRP, can declare a DLT if a patient is experiencing increasing toxicity during treatment, and it becomes clear that it is not going to be possible to complete the treatment without exposing the patient to excessive risk.

DLT-Equivalent Toxicity:

A DLT-equivalent toxicity is defined as an AE occurring between Day 1 and Day 28 of any cycle (other than Cycle 1) for a patient enrolled in Part A or in any cycle for a patient enrolled in

Dose Confirmation: Part B (including Cycle 1) that would have met the criteria for DLT if it had occurred during Cycle 1 for a patient enrolled in Part A.

Maximum Tolerated Dose (MTD):

For the purpose of this study, the MTD is defined as a safe dose that has the highest probability of DLT in the targeted toxicity interval (20 to 35%). A safe dose means that the probability of DLT larger than 35% is below 25%.

5.1.2. Efficacy Endpoints

The study was not designed to make an efficacy assessment. However, any tumor response data will be tabulated according to study part and patient cohort.

Response and progression will be evaluated in this study using the international criteria proposed by the New Response Evaluation Criteria in Solid Tumors (RECIST): Revised RECIST Guideline (version 1.1; Eisenhauer et al. 2009).

CCI
[Redacted]

CCI
[Redacted]

[Redacted]

5.2. Analysis Sets

Safety and efficacy analysis will be performed on all patients who receive at least 1 dose of study drug.

Pharmacokinetic (PK) analyses will be conducted on patients who have received at least 1 dose of the study drug and have had samples collected.

Pharmacodynamic (PD) analyses will be conducted on patients who have received at least 1 dose of the study drug and had PD assessments.

5.3. Statistical Methods

5.3.1. Sample Size Considerations

The total sample size for Parts A and B is estimated to be approximately 80 patients. In Part A, the sample size is estimated to be approximately 30 to 35 patients depending on the relationship between exposure and toxicity as well as the relationship between exposure and pharmacodynamic effects. A total of approximately 45 patients has been selected in the dose-confirmation phase to ensure an adequate sample size for assessing the safety, PK, and preliminary efficacy signals. The sample size of 15 for each confirmation cohort provides a reasonable power to explore preliminary signals of efficacy. If we assume that a true overall response (complete response [CR] + partial response [PR]) rate less than 10% indicates inadequate anti-tumor activity, then at a one-sided type 1 error rate of 5%, the sample size of 15 will provide 73% power if the true overall response rate is 30% or higher.

5.3.2. Dose Escalation Method

In this study, the escalation will start from the lowest planned dose, the maximum allowed dose increment is 100%, and each new dose level will have a minimum of 3 patients enrolled to it. The Bayesian model-based toxicity band method (Neuenschwander et al 2008) that incorporates prior expectations about the dosetoxicity curve will be fitted to the data at the end of each cohort to recommend a dose for the next cohort. The toxicity band method is a Bayesian model-based design with built-in escalation with overdose control mechanism. After each cohort, the toxicity band model will utilize data from all available cohorts to make dose recommendation, based on the model based posterior probability of a DLT at each dose, and the overdose control criteria. The toxicity band method will stop if the pre-specified maximum number of subjects is reached or the recommended next dose has been taken by 9 patients.

During the escalation, the investigators and Lilly CRP will consider both the model recommendation and the observed DLT rate at each cohort to determine the next dose level and determine when to stop the escalation. Dose levels for each cohort will not exceed those recommended by the toxicity band model. Dose escalation will take into account PK and PD information when available. Additional patients may therefore be enrolled at a specific dose level to characterize PK/PD.

Intermediate or higher dose levels will be explored if deemed necessary after discussion between the sponsor and investigators. The JBDA toxicity band model has the ability to accommodate additional dose levels naturally.

Details regarding the JBDA toxicity band design are provided in Protocol Attachment 10.

5.3.3. Treatment Compliance

Patient compliance with study drug will be assessed at each visit by direct questioning, patient's diary examination and counting returned capsules. Deviation(s) from the prescribed dosage regimen should be recorded on the case report form (CRF).

The patient must take $\geq 75\%$ of the intended doses to be deemed compliant with study drug

administration. Similarly, a patient may be considered noncompliant if he or she is judged by the investigator to have intentionally or repeatedly taken more than the prescribed amount of medication. Potential discontinuation of a patient due to study drug noncompliance will be discussed between the investigator and the Lilly CRP before making the final determination for discontinuation.

5.3.4. Interim Analyses

During Part A, patient safety will be assessed prior to each dose escalation to ensure nothing precludes administration of larger doses to future study patients. In addition to reviewing AEs and laboratory measurements, available PK/PD profiles of LY3009120 will be reviewed per cohort. Based on these interim results, modifications (eg, reductions in dose increment or changes in dosing schedule) to the dose-escalation strategy or other design elements may be made to ensure patient safety. The study investigators and the Lilly CRP will make the determination regarding dose escalation based upon their review of the safety/tolerability data and the PK data from the previous cohorts. In addition, an interim review will be conducted prior to proceeding to Part B including safety, PK, and PD. All relevant data will be reviewed to confirm the estimation of the MTD. The decision to proceed to Part B will be made following discussions between the investigators and Lilly clinical research personnel.

During Part B, interim analyses may be conducted in each cohort to review available safety, PK, PD, and efficacy data once enrollment to that particular cohort (A, B, or C) has completed and all evaluable patients in that cohort have either completed 3 cycles of therapy or discontinued from the treatment.

5.4. General Considerations

Statistical analysis of this study will be the responsibility of Eli Lilly and Company. The analyses for this study will be descriptive, except for possible exploratory analysis as deemed appropriate. Data analyses will be provided by dose groups and for all study patients combined wherever appropriate. For continuous variables, summary statistics will include number of patients, mean, median, standard deviation, minimum, and maximum. Categorical endpoints will be summarized using number of patients, frequency, and percentages. Missing data will not be imputed.

The interpretation of the study results will be the responsibility of the investigator with the Lilly CRP or CRS, pharmacokineticist, and statistician. The CRP or CRS and statistician will also be responsible for the appropriate conduct of an internal review for both the final study report and any study-related material to be authorized by Lilly for publication.

Exploratory analyses of the data not described below will be conducted as deemed appropriate.

5.5. Patient Disposition

All patient discontinuations (treatment and study) will be documented, and the extent of each patient's participation in the study will be reported. If known, a reason for their discontinuation will be given. All patients entered in the study will be accounted for in the summary of

disposition. The number of patients who do not qualify for analysis, who die, or who discontinue before treatment begins will be specified.

All significant protocol deviations will be listed by pre-determined categories (e.g., inclusion/exclusion criteria, noncompliance with protocol procedures, drug dosage/intervention, use of excluded treatments, informed consent/assent process, continuing after meeting withdrawal criteria, or other).

5.6. Patient Characteristics

Patient characteristics will include a summary of the following:

- Patient demographics
- Baseline disease characteristics
- Prior disease-related therapies
- Concomitant medications.

Other patient characteristics will be summarized as deemed appropriate.

5.7. Efficacy Analyses

The study was not designed to make an efficacy assessment. However, any tumor response data will be tabulated according to study part and patient cohort. A listing of best overall response will be provided by part and cohort. A summary of best overall response will be summarized by dose (Part A) and overall by study part. The percentage of patients with a confirmed response, defined as a complete response (CR) or partial response (PR), will be provided along with a 90% exact confidence interval for the response percentage. The objective response rate is defined as:

$(\# \text{ patients with confirmed CR or PR}) / (\# \text{ patients dosed with study drug})$

5.8. Safety Analyses

All patients who receive at least 1 dose of LY3009120 will be evaluated for safety and toxicity. Adverse event terms and severity grades will be assigned by the investigator using CTCAE, Version 4.0).

Safety analyses will include summaries of the following:

- adverse events, including severity and possible relationship to study drug
- dose adjustments
- laboratory values
- vital signs
- DLTs at each dose level
- ECG readings

In addition, after each cohort, the toxicity-band method will be used to summarize the posterior distribution of probability of a DLT.

5.8.1. Study Drug Exposure

Study drug exposure information will be listed by patient and summarized by dose (Part A) and overall by study part.

Number of capsules taken for each capsule strength will be listed, and the actual dose taken (mg) will be calculated for each cycle and all scheduled days within cycle for each patient.

A patient is said to have received a cycle if they received any of the doses in the cycle. The number of cycles given per patient will be summarized. Any dose adjustments will be characterized by presenting cycle delays, dose reductions, dose delays, and dose omissions, including reasons.

Dose intensity is defined as the percentage of the actual cumulative dose (mg) with respect to the planned cumulative dose (mg). Dose intensity will be listed per cycle and overall for all patients on therapy. Note that the denominator is based only on the assigned dose at the beginning of the cycle and not any additional prescribed reductions that may occur during the cycle.

Compliance for the study can be calculated by summing the doses across all cycles and dividing by the sum of the assigned dose for each cycle.

5.8.2. Dose Limiting Toxicity

Dose limiting toxicities (DLT) will be listed for all patients on therapy in Part A. DLT-equivalent toxicities will also be listed for all patients on therapy in Parts A and B. A Toxicity Band method (described in Protocol Appendix 10) will be used to assist the decisions related to dose escalation and determination of the MTD.

5.8.3. Adverse Events

CTCAE v4.0 will serve as the reference document for choosing appropriate terminology for, and grading the severity of, all AEs and other symptoms. For AEs without matching terminology within the CTCAE v4.0 criteria, the investigator will be responsible for selecting the appropriate system organ class and assessing severity grade based on the intensity of the event. Note that both CTCAE term (actual or coded) and severity grade must be selected by study site personnel and collected on the CRF. This collection is in addition to verbatim text used to describe the AE. In addition to collecting the AE verbatim, the CTCAE term, and the CTCAE severity grade, AE verbatim text will also be mapped by the sponsor or designee to corresponding terminology within the Medical Dictionary for Regulatory Activities (MedDRA) dictionary.

The investigator decides whether he or she interprets the observed AEs as either related to disease, to the study medication, study procedure, or other concomitant treatment or pathologies. To assess the relationship of the AE to the study drug, the following terminologies are defined:

- **Related:** a direct cause and effect relationship between the study treatment and the AE is likely.
- **Possibly Related:** a cause and effect relationship between the study treatment and the AE has not been demonstrated at this time and is not probable, but is also not impossible.
- **Unrelated:** without question, the AE is definitely not associated with the study treatment.

As per Lilly's standard operating procedures all "related" and "possibly related" AEs and SAEs

will be defined as related to study drug.

All AEs and SAEs, regardless of relatedness to study drug or protocol procedures, occurring during the follow-up visit (Visit 801) must be reported to Lilly or its designee. Following Visit 801, along-term follow-up will begin for dermatological assessment. Dermatological assessment will be performed every 2 months up to 6 months post-treatment discontinuation (long-term followup Visits 802, 803, and 804), after which the patient will be discontinued from the study, unless there is an ongoing AE or SAE that is possibly related to study drug. In this instance, the patient should be followed in subsequent follow-up visits, until the event is resolved, the event is no longer considered to be drug-related, the event becomes stable or returns to baseline, a new treatment is initiated for the patient, or the patient dies or is lost to follow-up. During the longterm follow-up period (V802 to V804), ongoing or new AEs/SAEs possibly related to study drug(s) or protocol procedures are required to be reported. After V804, if an additional follow-up period is necessary, new or ongoing AEs and new SAEs are not required to be reported, unless the investigator feels the events were related to either study drug, drug delivery system, or a protocol procedure.

Treatment emergent adverse events (TEAEs) are defined as AEs that first occurred or worsened in severity after the administration of at least one dose of study therapy, regardless of causality. New adverse events reported after Visit (801) will not be considered as a TEAE. With version4 CTCAE v4.0, the CTCAE codes are MedDRA LLT codes.

MedDRA mapping is applied to adverse event data as it is received. MedDRA versions may be upgraded as frequently as twice in a year. Therefore, different MedDRA versions may be used in this trial, based upon when the adverse event information is received, however, the safety information will be summarized and listed in preferred terms of the most current version of MedDRA at the time of reporting. Safety information collected with previous versions of MedDRA will be updated at the preferred term (PT) and system organ class level to the most currentversion in the locked database. The version used in any reports will be documented.

Specific tables and listings needed include:

- List of DLTs and DLT-equivalent toxicities
- List of pre-existing conditions and AEs
- List of serious AEs
- List of deaths
- Summary of AEs
- Summary of TEAEs
- Summary of related TEAEs
- listing of discontinuation due to AE or death
- summary of TEAE by maximum CTCAE grade
- summary of related TEAE by maximum CTCAE grade.

A separate listing of vomiting adverse events with dosing information included will also be produced.

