8.1.2.2.3. Follow-Up Visit

All AEs and SAEs, regardless of relatedness to study drug or protocol procedures, occurring during the follow-up visit (Visit 801) must be reported to Lilly or its designee. The follow-up visit starts following the last dose of study drug. At the end of the follow-up visit, the patient will be required to have specific safety assessments ([Attachment 1](#)). The timing of these safety assessments is 30 ± 3 days after the last dose of study drug.

Following the safety assessments, which mark the end of the first follow-up visit (Visit 801), a long-term follow-up will begin for dermatological assessment. Dermatological assessment will be performed every 2 months up to 6 months post-treatment discontinuation (long-term follow-up Visits 802, 803, and 804), after which the patient will be discontinued from the study, unless there is an ongoing AE or SAE that is possibly related to study drug. In this instance, the patient should be followed in subsequent follow-up visits, until the event is resolved, the event is no longer considered to be drug-related, the event becomes stable or returns to baseline, a new treatment is initiated for the patient, or the patient dies or is lost to follow-up. During the long-term follow-up period (V802 to V804), ongoing or new AEs/SAEs possibly related to study drug(s) or protocol procedures are required to be reported.

After V804, if an additional follow-up period is necessary, new or ongoing AEs and new SAEs are not required to be reported, unless the investigator feels the events were related to either study drug, drug delivery system, or a protocol procedure.

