8.1.3.2. Dermatological Safety Monitoring

New primary cutaneous malignancies have been reported with B-Raf inhibitors. Although LY3009120 is a pan-Raf inhibitor, which may mitigate some of the increased risk of cutaneous

malignancies hypothesized to be related to paradoxical Ras activation by B-Raf inhibition, dermatological evaluations will be performed as specified in the Study Schedule ([Attachment 1](#)) (at baseline, every 2 cycles while on therapy, and for up to 6 months following discontinuation of LY3009120).

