Relative Day Within a Cycle	1	8	15	22	28	1	8	15	22	28	1	28	Visit 801	Visits 802, 803, and 804 (Long-term Follow-up)	Visit 801 is 30 days (\pm 3 days) after last dose of study drug; Visits 802, 803, and 804 are each 2 months in duration and will start after Visit 801.
Pharmacogenetic blood sample, stored (mandatory)	X														
Exploratory blood plasma sample				X						X		X	X		To be collected in all patients in Part B for a maximum of 9 to 12 cycles.
Study Tumor Biopsy			X												Can be \pm 5 days

Abbreviations: BP = blood pressure; CTCAE = Common Terminology Criteria for Adverse Events; ECG = electrocardiogram; ECOG = Eastern Cooperative Oncology Group; PK = pharmacokinetic; PD = pharmacodynamic; PR = pulse rate; RR= respiration rate.

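### The TEAE cut-off in SAP 5.8.3 is keyed to reporting rather than onset, and it leaves related events first reported at Visits 802 to 804 out of the related-TEAE tables

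*SAP*

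**What the plan says.** SAP 5.8.3 (Adverse Events) first defines TEAEs as "AEs that first occurred or worsened in severity after the administration of at least one dose of study therapy, regardless of causality". That sentence turns on occurrence and sets no end date. The next sentence sets one: "New adverse events reported after Visit (801) will not be considered as a TEAE". It makes no exception for related events.

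Protocol 8.1.2.2.3 (Follow-Up Visit) fixes the visit: "The timing of these safety assessments is 30 ± 3 days after the last dose of study drug". After it, a "long-term follow-up will begin for dermatological assessment", made up of Visits 802, 803 and 804. In that period "ongoing or new AEs/SAEs possibly related to study drug(s) or protocol procedures are required to be reported", and SAP 5.8.3 repeats this requirement. Both documents class possibly related events as related to study drug. The background to the skin monitoring is in Protocol 8.1.3.2: "New primary cutaneous malignancies have been reported with B-Raf inhibitors".

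The list of outputs in SAP 5.8.3 contains two tables of related events, a summary of related TEAEs and the same by maximum CTCAE grade. Both are restricted to TEAEs. The list also names an AE listing, a serious AE listing and a summary of AEs whose content is not described. SAP 5.8.4 plans only a listing for the dermatological assessments. SAP 5.8 and Protocol 10.4 promise AE summaries that cover severity and relationship, with no TEAE restriction and no stated window.

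**The concern.** Two adjoining sentences use different clocks. The definition asks when an event began, and the exclusion asks when it was reported. An event that began on treatment but first came to light at Visit 802 satisfies the first and is barred by the second.

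The exclusion also falls on the type of event that the later visits are there to find. After Visit 801 the only new AEs that must be collected are those possibly related to drug or procedure, and the visits are dermatological. A new drug-related skin cancer found there would be recorded but would not count in either specified table of related events.

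Characterising the safety and toxicity profile is a secondary objective. A reader of the report will usually take the related-TEAE tables as the incidence of drug-related toxicity, and for delayed events those tables would be incomplete.

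**Working it through.** The plan states no figure on this point, so there is nothing to reproduce. The check follows single events through the text and then sizes the windows.

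**Step 1. Three example events**

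- *Possibly related cutaneous malignancy, onset after Visit 801, first reported at Visit 803.* It meets the occurrence definition, must be reported under Protocol 8.1.2.2.3, and counts as related. The cut-off sentence makes it a non-TEAE. It is therefore absent from the related-TEAE summary and the related maximum-grade table. It is present in the AE listing, the dermatological listing and, if serious, the serious AE listing. Its place in the summary of AEs and in the SAP 5.8 summaries is not specified.
- *Related AE, onset before Visit 801, first reported at Visit 802.* The result is the same, although its onset lies inside the window.
- *AE already reported by Visit 801 that worsens later.* It is not new, so the cut-off sentence does not bar it.

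**Step 2. Share of scheduled monitoring time after the cut-off**

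Inputs:

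- T, days on treatment: 2 planned cycles of 28 days = 56 (Protocol 6.2). As an alternative, 5 cycles = 140, the average used for blood volumes in Attachment 8.
- V, Visit 801: day 30 after the last dose.
- E, end of dermatological follow-up, counted from the last dose. The documents give two readings. SAP 5.8.3 says "Dermatological assessment will be performed every 2 months up to 6 months post-treatment discontinuation", so E = 6 × 30 = 180 days. Attachment 1 says "Visits 802, 803, and 804 are each 2 months in duration and will start after Visit 801", so E = 30 + 3 × 60 = 210 days.

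Share outside the TEAE window = (E − V) / (T + E).

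| Cycles | E = 180 | E = 210 |
|---|---|---|
| 2 (T = 56) | 150 / 236 = 64% | 180 / 266 = 68% |
| 5 (T = 140) | 150 / 320 = 47% | 180 / 350 = 51% |

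For the post-treatment period alone, (E − V) / E gives 150 / 180 = 83% and 180 / 210 = 86%.

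The ± 3 days on Visit 801 matter little. At 2 cycles the first reading runs from 147 / 236 = 62% to 153 / 236 = 65%, and the second from 180 / 269 = 67% to 180 / 263 = 68%. Using months of 30.44 days instead of 30 moves each share by less than half a percentage point.

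**Step 3. What one patient is worth**

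One excluded patient lowers a related-TEAE incidence by 1 / 80 = 1.25 points over the whole study, or 1 / 45 = 2.2 points in Part B. This holds only if that patient has no other event counted in the same row.

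The documents give no rate of late related events. If 2%, 5% or 10% of 80 patients had one (pure assumption), the expected number excluded would be 1.6, 4.0 or 8.0.

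**The case against.** The strongest reply is that a Visit 801 cut-off is sound for all-causality TEAEs. Through Visit 801 every AE is collected regardless of relatedness; afterwards only possibly related ones must be. Closing the window where collection narrows keeps ascertainment uniform. That stands, and the all-causality tables need no longer window. It does not explain why related events, which are collected through Visit 804, have no specified incidence table, or why the boundary is set by reporting.

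A second reply is that other outputs cover the gap. SAP 5.8 and Protocol 10.4 promise AE summaries by severity and relationship without a TEAE restriction, and the list of outputs in SAP 5.8.3 is not presented as exhaustive. This also stands in part. A reader might infer that late related events are lost or can enter no summary, and the documents do not support that. They do leave it open whether any summary includes Visits 802 to 804.

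Third, the wording may simply mean the visit period, so that late reporting of an early event was never in view. That is possible, but the literal text says otherwise, and a programmer will follow the text.

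Fourth, a reader might turn the 68% into a claim that two thirds of new skin lesions would be excluded. That needs a constant hazard on and off drug, which no document supports. It also assumes 2 cycles, the longer reading of follow-up, and full follow-up. Patients with benefit may continue beyond 2 cycles. Many will stop for progression, and entry requires an estimated life expectancy of only 12 weeks. Lesions reported on treatment or by Visit 801 remain TEAEs.

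**Conclusion.** The point holds in a limited form. On the literal text of SAP 5.8.3, a new drug-related AE first reported after Visit 801 is left out of both specified related-event tables, whatever its onset date. The cut-off also conflicts with the occurrence-based definition in the sentence before it.

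The affected share of scheduled monitoring time is about 64% to 68% at 2 cycles and about 47% to 51% at 5 cycles, taking 30-day months, Visit 801 at day 30 and complete follow-up. These are shares of time, not of events; the number of events affected cannot be derived from the documents.

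The gap concerns a secondary, descriptive objective. The MTD rests on Cycle 1 DLTs and is not touched. The point is worth correcting because the data are already to be collected and the correction is small.

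**What to change.** 1. In SAP 5.8.3, keep the Visit 801 window for all-causality TEAEs but define it by AE onset date instead of reporting.
2. Add one incidence table, by dose and by maximum CTCAE grade, of AEs related to study drug with onset through Visit 804. Include related new primary cutaneous malignancies.
3. Reconcile the two descriptions of the long-term follow-up: up to 6 months after treatment discontinuation (Protocol 8.1.2.2.3, SAP 5.8.3) and three 2-month visits starting after Visit 801 (Protocol Attachment 1). The end of the new table's window depends on this.

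The cost is one changed sentence, one extra table and a footnote. The footnote should say that the table's window is longer than the TEAE window and that after Visit 801 only possibly related events are required to be reported. No new data or visits are needed as long as the table is confined to related events. Counting every new malignancy through Visit 804, including those judged unrelated, would need a change to AE collection in the protocol, so it is not proposed here.
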